6.4.8 Psoriasis Area and Severity Index (PASI)

The PASI (Fredriksson 1978; Weisman 2003; Gottlieb 2005) assesses the extent of psoriasis on four body surface areas (head, trunk and upper and lower limbs) and the degree of plaque erythema, scaling and thickness. A PASI score will be derived as indicated in Table 6-3.

The head, trunk, upper limbs and lower limbs are assessed separately for erythema, thickening (plaque elevation, induration) and scaling (desquamation). The average degree of severity of each sign in each of the four body regions is assigned a score of 0-4. The area covered by lesions on each body region is estimated as a percentage of the total area of that particular body region. Further practical details help the assessment:

- The neck is assessed as part of the head.
- The axillae and groin are assessed as part of the trunk.
- The buttocks are assessed as part of the lower limbs.

When scoring the severity of erythema, scales should not be removed.

Table 6-3 The PASI scoring system

Body region	Erythema	(E)	Thickening (plaque elevation, induration, I)	Scaling (desquamation, D)	Area score (based on true area%, A)*
Head (H) [†]	0=none		0=none	0=none	0 = no involvement
	1=slight 2=moderate		1=slight 2=moderate	1=slight 2=moderate	1 = >0-< 10%
	3=severe 4=very severe		3=severe 4=very severe	3=severe 4=very severe	2 = 10-<30%
	•		-	-	3 = 30-<50%
					4 = 50-<70%
					5 = 70-<90%
					6 = 90-100%
Trunk (T) [‡]	0=none		0=none	0=none	0 = no involvement
	1=slight 2=moderate		1=slight 2=moderate	1=slight 2=moderate	1 = >0-< 10%
	3=severe 4=very severe		3=severe 4=very severe	3=severe 4=very severe	2 = 10-<30%
					3 = 30-<50%
					4 = 50-<70%
					5 = 70-<90%
					6 = 90-100%
Upper	0=none		0=none	0=none	0 = no involvement
limbs (U)	1=slight 2=moderate		1=slight 2=moderate	1=slight 2=moderate	1 = >0-< 10%
	3=severe 4=very severe		3=severe 4=very severe	3=severe 4=very severe	2 = 10-<30%
					3 = 30-<50%
					4 = 50-<70%
					5 = 70-<90%
					6 = 90-100%

Body region	Erythema	(E)	Thickening (plaque elevation, induration, I)	Scaling (desquamation, D)	Area score (based on true area%, A)*
Lower	0=none		0=none	0=none	0 = no involvement
limbs (L) [§]	1=slight 2=moderate		1=slight 2=moderate	1=slight 2=moderate	1 = >0-< 10%
	3=severe 4=very severe		3=severe 4=very severe	3=severe 4=very severe	2 = 10-<30%
					3 = 30-<50%
					4 = 50-<70%
					5 = 70-<90%
					6 = 90-100%

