^{*} Percentage (not score) of body region (not whole body) affected will be entered in the eCRF

The head and neck, upper limbs, trunk and lower limbs correspond to approximately 10%, 20%, 30% and 40% of the body surface area, respectively; the PASI score is calculated using the following formula:

$$PASI = 0.1(E_H + I_H + D_H)A_H + 0.2(E_U + I_U + D_U)A_U + 0.3(E_T + I_T + D_T)A_T + 0.4(E_L + I_L + D_L)A_L$$

where E = erythema; I = induration; D = desquamation; A = area; H = Head; U = Upper limbs; T = Trunk; and L = Lower limbs

PASI scores can range from a lower value of 0, corresponding to no signs of psoriasis, up to a theoretic maximum of 72.0. The investigator is responsible for collecting the components or scoring signs and total regional area. More information is provided in Appendix 5.

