The PASI is a system used for assessing and grading the severity of psoriatic lesions and their response to therapy. The PASI produces a numeric score that can range from 0 to 72. The severity of disease is calculated as follows. In the PASI system, the body is divided into 4 regions: the head (h), trunk (t), upper extremities (u), and lower extremities (l), which account for 10%, 30%, 20% and 40% of the total BSA, respectively. Each of these areas is assessed separately for erythema, induration and desquamation (scaling), which are each rated on a scale of 0 to 4. The scoring system for the signs of the disease (erythema, induration, and desquamation (scaling)) are:

0 = none; 1 = slight; 2 = moderate; 3 = severe; and 4 = very severe.

The scale for estimating the area of involvement for psoriatic lesions is outlined below.

0 = no involvement

1 = 1% to 9% involvement

2 = 10% to 29% involvement

3 = 30% to 49% involvement

4 = 50% to 69% involvement

5 = 70% to 89% involvement

6 = 90% to 100% involvement

To help with the area assessments, the following conventions should be noted:

- the neck is considered part of the head
- the axillae and groin are part of the trunk
- the buttocks are part of the lower extremities

The PASI formula is: PASI = 0.1 (Eh + Ih + Dh) Ah + 0.3 (Et +It+ Dt) At+ 0.2 (Eu + Iu + Du) Au+ 0.4 (El +II+ Dl) AI (where E= erythema, I = induration, D = desquamation and A = area)

Table 17-1 PASI Scoring Worksheet

	Head	Upper extremities	Trunk	Lower extremities
Redness †				
Thickness †				
Scale †				
Sum of rows 1, 2, and 3				
Area score ‡				
Score of row 4 x row 5 x the area multiplier	Row 4 x row 5 x 0.1	Row 4 x row 5 x 0.2	Row 4 x row 5 x 0.3	Row 4 x row 5 x 0.4
Sum row 6 for each column for PASI score				

- a. Divide body into four areas: head, arms, trunk to groin, and legs to top of buttocks.
- b. Generate an average score for the erythema, thickness, and scale for each of the 4 areas (0=clear, 1-4=increasing severity).
- c. Sum scores of erythema, thickness, and scale for each of the 4 area.
- d. Generate a percentage for skin covered with psoriasis for each area and convert that to a 0-6 scale. ‡
- e. Multiply score of item c above times item d above for each area and multiply that by 0.1, 0.2, 0.3 and 0.4 for head, arms, trunk, and legs, respectively.
- f. Add these scores to get the PASI score.
- † Erythema, thickness, and scale are measured on a 0-4 scale (none, slight, mild, moderate, severe)

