****Buttocks are assessed as part of the Lower limbs (L) body region.

[figure not shown]
Because the head and neck, upper limbs, trunk and lower limbs correspond to approximately 10%, 20%, 30% and 40% of the body surface area, respectively, the PASI score is calculated using the formula:

[figure not shown]
$$\text{PASI} = 0.1(\text{E}_H + \text{I}_H + \text{D}_H)\text{A}_H + 0.2(\text{E}_U + \text{I}_U + \text{D}_U)\text{A}_U + 0.3(\text{E}_T + \text{I}_T + \text{D}_T)\text{A}_T + 0.4(\text{E}_L + \text{I}_L + \text{D}_L)\text{A}_L$$

[figure not shown]
The keys for the letters are provided in [Table 2-7](#).

[figure not shown]
PASI scores can range from a lower value of 0, corresponding to no signs of psoriasis, up to a theoretic maximum of 72.0. The total score comes from eCRF.

3 Sample size calculation

A family-wise error will be set to two-sided $\alpha=0.05$ to control for type I error. The primary objective of secukinumab 300 mg versus adalimumab with respect to ACR50/ACR20 response at Week 52 will be tested at a two-sided 0.05 alpha level.

An ACR20 response rate of about 50% for the TNF α inhibitor naïve without MTX use (monotherapy) population at week 48 was reported in Humira study ([Gladman 2007](#)). The response on secukinumab 300 mg is estimated to be 62% in the TNF α inhibitor naïve monotherapy population based on the lower bound of 80% confidence interval of Meta-analysis results of the study FUTURE2 ([McInnes 2015](#)) and unpublished study FUTURE3. With 425 subjects per treatment group there would be approximately 94% power to detect a treatment difference of 12% at a two-sided 0.05 alpha level in ACR20 response rates (Chi Square test, NQuery 7.0) between secukinumab 300 mg and adalimumab in the evaluation of the primary efficacy hypothesis at Week 52. The overall sample size will be 850 patient for a randomization ratio of 1:1 (secukinumab 300mg 425 patients, and adalimumab 425 patient). The estimated power with the chosen sample size for other efficacy endpoints based on the data available for adalimumab and meta-analysis results of the study FUTURE2 and study FUTURE3 are summarized in [Table 3-2](#).

Table 3-1 Assumption for sample size and power calculation

Endpoint	Secukinumab 300 mg expected values	Adalimumab (N=76) observed values
ACR20	62%	50%
PASI90	63%	38% (N=40)
ACR50	49%	38%
HAQ-DI change*	-0.59 (0.5)	-0.4 (0.5)(N=61)
Resolution of enthesitis	61%	33%

*mean (standard deviation)

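### Does the mismatched severity wording under the Appendix 5 PASI worksheet put the PASI90 result at risk?

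*Protocol*

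**What the plan says.** Protocol Section 6.4.8 names the source of the score: "A PASI score will be derived as indicated in Table 6-3". In that table the upper two sign scores are "3=severe 4=very severe" for each of the four body regions, with slight as 1 and moderate as 2. SAP Section 2.12.3.1 repeats these anchors in Table 2-7. Section 6.4.8 then refers to the appendix only as background: "More information is provided in Appendix 5".

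Appendix 5 contains two word lists. The key in its text is numbered: "0 = none; 1 = slight; 2 = moderate; 3 = severe; and 4 = very severe". The footnote to the worksheet's redness, thickness and scale rows is not: "Erythema, thickness, and scale are measured on a 0-4 scale (none, slight, mild, moderate, severe"). Step b of the worksheet instructions scores severity by number alone, with 0 for clear skin and 1 to 4 for rising severity.

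On data capture, worksheet step d tells the user: "Generate a percentage for skin covered with psoriasis for each area and convert that to a 0-6 scale". The note under Table 6-3 says something different about what is recorded: "Percentage (not score) of body region (not whole body) affected will be entered in the eCRF". The SAP says of the PASI total: "The total score comes from eCRF".

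**The concern.** The footnote is more than a choice of synonyms. It adds *mild*, drops *very severe*, and moves two shared words up one place. By order in the list, *moderate* becomes 3 instead of 2 and *severe* becomes 4 instead of 3, while *none* and *slight* stay put. Because the shift is uneven, it need not cancel in a percentage change from baseline, and a patient near the 90% threshold could change status.

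PASI90 is H2 in the hierarchy, and H3 to H5 are tested only if H2 is rejected. The SAP takes the total from the eCRF, so the analysis could neither detect nor undo a mix-up in the labels.

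**Working it through.** **1. The lists side by side**

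| Score | Numbered key, Table 6-3, SAP Table 2-7 | Worksheet footnote, read in order |
|---|---|---|
| 0 | none | none |
| 1 | slight | slight |
| 2 | moderate | mild |
| 3 | severe | moderate |
| 4 | very severe | severe |

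Scores 0 and 1 agree; 2, 3 and 4 differ in wording only. The scale runs from 0 to 4 in both, and the formula uses the numbers. The maximum is (0.1 + 0.2 + 0.3 + 0.4) × (4 + 4 + 4) × 6 = 72 under either list, which matches the stated range.

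**2. When can a score change?**

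A rater who uses either list alone, as five ordered steps, can give the same lesion the same number. A change needs a mixed reading: the Table 6-3 meaning of the word, with the number taken from the footnote's order.

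**3. What a mixed reading would do**

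These are constructed patients with one region involved, so the region weight cancels. Score = sum of the three signs × area score; improvement = 1 − Week 52 score / baseline score. *Very severe* is absent from the footnote and is assumed to stay at 4.

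- *Patient A.* Baseline severe on three signs, area 3: 9 × 3 = 27 on Table 6-3, or 12 × 3 = 36 on the mixed reading. Week 52 slight on three signs, area 1: 3 on both. Improvement is 1 − 3/27 = 88.9% against 1 − 3/36 = 91.7%. A non-responder becomes a responder, even though both visits are read in the same way.
- *Patient B.* Baseline as for A. Week 52 one moderate sign, area 1: 2 on Table 6-3, or 3 mixed. Improvement is 1 − 2/27 = 92.6% on Table 6-3. Mixed at both visits it is 1 − 3/36 = 91.7%, still a responder. Mixed at Week 52 only it is 1 − 3/27 = 88.9%, a non-responder.
- *Patient C.* Baseline very severe on three signs, area 3: 36 on both. Week 52 one severe sign, area 1: 3 on Table 6-3, or 4 mixed. Improvement is 1 − 3/36 = 91.7% against 1 − 4/36 = 88.9%. A responder is lost, again with the same reading at both visits.

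The effect can therefore go either way. In a grid of 12 constructed cases (baseline moderate or severe on all signs, area 2 or 3, one to three slight signs at Week 52, mixed reading at both visits), 9 kept their PASI90 status.

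**4. What it would do to H2**

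Inputs: 63% against 38% (protocol Table 9-1), 213 per group (footnote to Table 9-2), two-sided alpha 0.05, chi-square test with pooled variance under the null. This gives power 0.9995, consistent with the 99% in Table 9-2. The misclassification rates below are assumptions, equal in both arms.

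| Assumed 10% rate | Secukinumab | Adalimumab | Power |
|---|---|---|---|
| Responders lost | 0.63 × 0.9 = 0.567 | 0.38 × 0.9 = 0.342 | 0.997 |
| Non-responders gained | 0.63 + 0.1 × 0.37 = 0.667 | 0.38 + 0.1 × 0.62 = 0.442 | 0.997 |
| Both | 0.567 + 0.037 = 0.604 | 0.342 + 0.062 = 0.404 | 0.987 |

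At 2% or 5% in one direction, power is 0.999.

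**The case for a change.** The best case for acting is that a protocol should carry one set of anchors for an endpoint in the confirmatory hierarchy. The stray list sits under the very rows a rater would fill in, and Section 6.4.8 does send readers to that appendix. Patients A and C show that even a rater who errs consistently can change a patient's status. The documents do not show which labels the eCRF or the training material display, so only the sponsor can exclude an effect, and correcting a single line looks cheap.

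The wording mismatch stands, as does the limit on what the documents can settle about the eCRF. The step from there to a needed change does not. Wherever the documents attach numbers to these words, they give the Table 6-3 anchors, and one of those places is the key in the same appendix. Nothing shows that the worksheet is the capture form: it converts area to a 0-6 score, whereas the eCRF takes the percentage. Nor is the correction quite free, because protocol Section 11.1 requires a written amendment for any change. An amendment made for this line alone would not improve the PASI90 analysis.

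**Conclusion.** This is a clerical slip in an unnumbered footnote. Following the plan as written, with scores taken from Table 6-3 and analysed under the matching SAP Table 2-7, gives a sound PASI90 result. The line is worth tidying if the protocol is amended for another reason, but nothing in the design, the analysis or the SAP depends on it.

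The possible effect is confined to patients near the 90% threshold whose rater mixed the two lists. The documents offer no basis for their number, which could be zero. Under the assumed rates of up to 10%, H2 power stays at 0.987 or higher, and ACR20 is untouched. The power figures assume that any mis-scoring is equal in the two arms. That is reasonable because protocol Section 5.4 keeps the persons performing the assessments blinded. The conclusion also assumes that the eCRF and rater training follow Table 6-3, as Section 6.4.8 directs; the documents available here cannot confirm this.

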AUC	Area Under the Curve
bid	bis in diem/twice a day
BMI	Body Mass Index
BP	Blood Pressure
BSL	Baseline
CASPAR	CIASSification criteria for Psoriatic ARthritis
cDMARD	conventional Disease modifying anti-rheumatic drugs (also known as nonbiologic DMARDs)
CRF	Case Report/Record Form (paper or electronic)
CRO	Contract Research Organization
CRP/hsCRP	C-reactive protein / high sensitivity C-reactive protein
CSR	Clinical Study Report
CTC	Common Toxicity Criteria
CTCAE	Common Terminology Criteria for Adverse Events
CV	Coefficient of Variation
████	████████████████████
████	██
DMARD	Disease Modifying Antirheumatic Drug
DMC	Data Monitoring Committee
ECG	Electrocardiogram
eCRF	Electronic Case Report/Record Form
████	██
ESR	Erythrocyte Sedimentation Rate
████	██
████████████████	██
FAS	Full Analysis Set
FDA	Food and Drug Administration
FSH	Follicle Stimulating Hormone
GCP	Good Clinical Practice
GEE	Generalized Estimating Equation
HAQ-DI	Health Assessment Questionnaire – Disability Index
HDL	High Density Lipoprotein
████	██
hsCRP	High sensitivity C-Reaction Protein
████████████████	██
IL	Interleukin

i.v.	Intravenous(ly)
IVR	Interactive Voice Response
IWR	Interactive Web Response
█	█
LDL	Low Density Lipoprotein
█	█
LLN	Lower Limit Normal
LLOQ	Lower Limit of Quantification
MAR	Missing at Random
█	█
█	█
█	█
MedDRA	Medical Dictionary for Drug Regulatory Affairs
█	█
mmHg	Millimeter mercury
MMRM	Mixed-effects Repeated Measures Model
█	█
MTX	Methotrexate
NSAID	Non-steroidal anti-inflammatory drug
█	█
PASI	Psoriatic Area and Severity Index
█	█
█	█
█	█
PoC	Proof of Concept
PRO	Patient-reported Outcomes
PsA	Psoriatic Arthritis
PsaQoL	Psoriatic Arthritis Quality of Life questionnaire
█	█
QoL	Quality of Life
RA	Rheumatoid Arthritis
RAP	Report and Analysis Process
RBC	Red Blood Cells
RF	Rheumatoid Factor
SAE	Serious Adverse Event
SAP	Statistical Analysis Plan
s.c.	Subcutaneous(ly)
SCE	Summary of Clinical Efficacy
SCS	Summary of Clinical Safety
SD	Standard Deviation
█	█
SJC	Swollen Joint Count
SNP	Single Nucleotide polymorphism

SpA	Spondyloarthritis
SOC	System Organ Class
TFLs	Tables, Figures, Listings
TJC	Tender Joint Count
TNF	Tumor Necrosis Factor
TNF-IR	TNF α Inhibitor Inadequate Responders
ULN	Upper Limit of Normal
VAS	Visual Analog Scale
WBC	White Blood Cells
WHO	World Health Organization

1 Introduction

Data will be analyzed by Novartis according to the data analysis section 9 of the clinical study protocol. The statistical methodology is described below and any deviations from the protocol are documented. Additional detailed information regarding the analysis methodology is contained in the Appendix section.

1.1 Study design

This is a randomized, double-blind, active control, multicenter, parallel-group trial evaluating secukinumab monotherapy and adalimumab monotherapy in approximately 850 subjects with active PsA. A screening period up to 8 weeks before randomization will assess subject eligibility. Efficacy assessments will occur through Study Week 52. Two follow-up visits at Week 60 and 68 will occur thereafter. Total maximum study duration, including screening period, is up to 76 weeks.

At Baseline, subjects whose eligibility is confirmed will be randomized to either Group 1 (secukinumab 300 mg as 2 x 150 mg s.c. injections), or Group 2 (adalimumab 40 mg as 1 s.c. injection) with approximately 425 subjects/group. In order to maintain the blind, both groups will receive 1 or 2 placebo s.c. injections to keep consistency in the number of injections at each dosing visit. Secukinumab is available in 150 mg/1.0 mL pre-filled syringes (PFS) and adalimumab is available in 0.4 mL PFS. Placebo (1.0 and 0.5 mL, PFS) is also available.

Group 1 - Secukinumab 300 mg s.c.

Secukinumab 300 mg (2 x 1 mL PFS) will be administered at Baseline, Weeks 1, 2, 3 and 4, followed by dosing every 4 weeks until Week 48. In addition, all Group 1 subjects will receive placebo (1 x 1mL PFS) at given visits in order to maintain the blind.

Group 2 - Adalimumab 40 mg s.c.

Adalimumab 40 mg (1 x 0.4 mL PFS) will be administered at Baseline followed by dosing every 2 weeks until Week 50. In addition, all Group 2 subjects will receive placebo (1 x 0.5mL or 2 x 0.5mL PFS) at given visits in order to maintain the blind.

1.2 Study objectives and endpoints

1.2.1 Primary objective

[figure not shown]
To demonstrate that the efficacy of secukinumab monotherapy 300 mg s.c. at Week 52 is superior to adalimumab monotherapy (40 mg s.c.) based on the proportion of subjects achieving an American College of Rheumatology 20 (ACR20) response.

1.2.2 Secondary objectives

To demonstrate that:

1. Secukinumab monotherapy (300 mg s.c.) is superior to adalimumab monotherapy (40 mg s.c.) at Week 52, based on the proportion of subjects achieving PASI90 response.
2. Secukinumab monotherapy (300 mg s.c.) is superior to adalimumab monotherapy (40 mg s.c.) at Week 52, based on the proportion of subjects achieving an ACR50 response.

3. The improvement (change) from baseline on secukinumab monotherapy (300 mg s.c.) is superior to adalimumab monotherapy (40 mg s.c.) at Week 52, for the Health Assessment Questionnaire – Disability Index (HAQ-DI©) score.
4. Secukinumab monotherapy (300 mg s.c.) is superior to adalimumab monotherapy (40 mg s.c.) at Week 52, based on the proportion of subjects achieving the resolution of enthesitis based on LEI.
5. An additional secondary objective is to evaluate the safety and tolerability of secukinumab monotherapy (300 mg s.c.) compared with adalimumab monotherapy (40 mg s.c.) as assessed by vital signs, clinical laboratory values, and adverse events monitoring.

2 Statistical methods

2.1 Data analysis general information

Summary statistics for continuous variables include N, mean, standard deviation, minimum, lower quartile, median, upper quartile, and maximum. For binary or discrete variables the absolute number of subjects in each category and relative frequencies will be provided.

Unless otherwise specified, p-values will be presented as 2-sided p-values and the type I error rate (alpha) will be 5%.

Inferential efficacy comparison of secukinumab 300mg with adalimumab will be performed at Week 52 unless otherwise specified.

Efficacy and safety data for the entire treatment period will be presented by treatment groups.

2.2 Analysis sets and treatment groups

The following analysis sets will be used for the data analysis.

Randomized set: The randomized set will be defined as all subjects who were randomized. Unless otherwise specified, mis-randomized subjects (mis-randomized in Interactive Voice Response (IVR)) will be excluded from the randomized set.

Mis-randomized subjects are defined as those subjects who were mistakenly randomized into the IVR prior to the site confirming all eligibility criteria had been met and to whom no study medication was given. Mis-randomized patients are treated as screen failures.

Full analysis set (FAS): The FAS will be comprised of all subjects from the randomized set to whom study treatment has been assigned. Following the intent-to-treat principle, subjects will be analyzed according to the treatment assigned to at randomization. Two subsets of FAS are defined as follows:

- Enthesitis subset (LEI): The enthesitis subset will include all FAS subjects who have enthesitis based on LEI at baseline.

[figure not shown]
- 
- Psoriasis subset: The psoriasis subset will include all FAS subject who have $\geq 3\%$ of the body surface area (BSA) affected by psoriatic skin involvement at baseline.

Safety set: The safety set includes all subjects who took at least one dose of study treatment during the treatment period. Subjects will be evaluated according to treatment received.

2.2.1 Treatment groups

The summaries by treatment will be performed by the randomized treatment.

Randomized treatment:

- AIN457 300 mg
 - Adalimumab 40 mg
- 

2.4 Patient disposition, demographics and other baseline characteristics

2.4.1 Patient disposition

The number of subjects screened will be presented. In addition, the reasons for screen failures will be provided. The number and percentage of subjects in the randomized set who completed the study periods and who discontinued the study prematurely (including the reason for discontinuation) will be presented at the end of the treatment period for each treatment group and all subjects.

For each protocol deviation (PD), the number and percentage of subjects for whom the PD applies will be tabulated.

2.4.2 Background and demographic characteristics

The following background and demographic variables will be analyzed:

Continuous variables:

- Age (which is derived from date of birth and the screening assessment date)
- Height
- Weight
- Body mass index (BMI) = (body weight in kilograms) / (height in meters)²

Categorical variables:

- Age categories (<65 years, 65 years and older, 75 years and older)
- Gender
- Race
- Ethnicity

The following disease specific baseline characteristics will be summarized by treatment groups:

- ACR components and other disease-related measures (e.g. [REDACTED], presence of enthesitis (based on LEI [REDACTED]), [REDACTED], time since first diagnosis of psoriatic arthritis, [REDACTED], subjects with psoriasis \geq 3%)

Unless otherwise specified, summary statistics will be presented for continuous variables for each treatment group and for all subjects (total) in the randomized set. The number and percentage of subjects in each category will be presented for categorical variables for each treatment group and all subjects (total) in the randomized set.

